The goal of this research is to examine the potential impact of alternative tobacco products on the use of conventional cigarettes, alone and in combination with nicotine replacement, to simulate a potential regulatory scenario in which a variety of tobacco and nicotine products are available that vary in degree of risk, similarity to cigarettes, and acceptability. Therefore, we opted to use two products that have shown potential to substitute for traditional cigarettes: very low nicotine content cigarettes (VLNCs) and the Juul e-cig.

VLNCs. Participants randomized to receive VLNCs will receive NIDA's reduced nicotine cigarettes with 0.03 (±0.01) mg of nicotine with a tar yield of 9±1.5 via NIDA's Drug Supply Program (NOT-DA-14-004). These cigarettes have been characterized by Richter and colleagues¹¹⁶. Participants will be able to choose either menthol or non-menthol VLNC's consistent with prior research (e.g., ¹⁰⁰) and to enhance the external validity of these findings. Participants will be instructed to smoke the VLNCs the same way they would their own cigarettes and will be given enough VLNCs to completely substitute for their own cigarettes during the Switch Weeks (i.e., if they smoke 20 cigarettes per day, they will receive enough VLNCs to be able to smoke 20 VLNCs per day).

One real-world safety concern with VLNC use is that it might result in compensatory smoking or oversmoking and increased exposure to carcinogens¹¹⁷. However, many studies have shown that smokers engage in minimal or no compensatory smoking^{73,82,83,102,118}. If participants in this condition need more VLNCs, they will be provided with additional VLNCs at subsequent study visits. However, we will monitor compensatory smoking by examining both VLNCs smoked/day as well as carbon monoxide (CO) levels. Participants found to be smoking more than twice their usual cigarettes/day or who demonstrate a CO \geq 100 ppm will be

"Understanding the real-world impact of the use of three alternate nicotine-delivery products on combustible cigarette use" PI: [name]; UW-CTRI Grant: R01CA239309

discontinued from the study protocol. Research has also shown that there is no increased risk with respect to cardiovascular biomarkers or exposure to toxicants among smokers using VLNCs^{67,97,119,120} and this study will produce a very brief exposure (i.e., only 4 weeks, which is less than the 6 weeks used by other studies^{67,83,97}).

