The primary aim of this research is to examine the ability of VLNCs and e-cigs to substitute for smokers' usual cigarettes compared to each other and to no alternative product use (Product between-subjects effects) and whether these effects are influenced by steadystate nicotine (Patch within-subjects factor; active vs. placebo patch). The primary analysis model will consist of a mixed analysis of variance (ANOVA) with three levels of the Product between-subjects factor (VLNCs, e-cigs, no alternative product) and two levels of the Patch within-subjects factor (active nicotine patch, placebo patch). To address the primary aim, we will explore statistically significant main or interaction effects in the mixed ANOVA by means of unadjusted simple main effects, interaction contrasts, and pairwise comparisons^{156,157}. Specifically, we will examine the main effect of Product to evaluate the hypothesis that participants who do not have an alternative product will report smoking significantly more of their own cigarettes during the Switch Weeks compared to those who have VLNCs or e-cigs. We will also conduct a pairwise comparison to explore whether there is a significant difference in the number of conventional cigarettes smoked in the VLNC vs. e-cig conditions. We will use the main effect of Patch (active vs. placebo) to evaluate the hypothesis that participants will report smoking fewer of their own cigarettes during Switch Weeks when they receive active nicotine patches compared to placebo patches. We will also test the Patch x Product interaction, with follow-up pairwise comparisons, to examine whether steady-state nicotine produces a differential effect on the number of conventional cigarettes smoked, based on which alternative product a participant was assigned to receive.

The primary outcome is the number of conventional cigarettes smoked during each Switch Week. Based on the literature and our own research, it is possible this outcome will not be normally distributed (i.e., a substantive proportion of participants may smoke no conventional cigarettes during a Switch Week). Therefore, prior to conducting main analyses, we will examine the distributional characteristics of the primary outcome to determine if a transformation is needed (e.g., if the distribution substantially deviates from a normal distribution).

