To facilitate safety, participants who are not be medically appropriate to use the nicotine patch will not be included in the study (e.g., no previous allergic reactions). Once enrolled, study protocols will assess side effects and unanticipated health events at all study visits and follow-up contacts. We will recommend using a lower dose patch or no patch if the participant experiences symptoms of nicotine toxicity or other troublesome side effects during their Switch Weeks. If participants in the VLNC condition are found to be smoking more than twice their usual cigarettes/day or have an exhaled $CO \ge 100$ ppm, they will be discontinued from the study protocol. We will refer participants their primary care provider as needed. Should excessive risk to study participants be determined, the study will be stopped and all participants notified in a manner appropriate to the nature of the risk.

Confidentiality of participant data and information will be accomplished by using participant ID numbers as unique identifiers, allowing us to keep participant data separate from identifying information. The UW-CTRI Information Technology Administrator, [name], manages the hardware, data, security, and infrastructure below the firewall. Access to the network is limited to only UW-CTRI owned and actively managed devices. All devices automatically lock and are password protected after 15 minutes of inactivity. All portable devices are encrypted for data security and no PHI is stored on local devices. All data stored on the network file server is limited by the principle of least privilege. With respect to the study smartphones, to provide confidentiality and HIPAA compliance, UW-CTRI uses MDM software (mobile device management software) in said study to protect and collect subject data. All

"Understanding the real-world impact of the use of three alternate nicotine-delivery products on combustible cigarette use" PI: [name]; UW-CTRI Grant: R01CA239309

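### The VLNC-only discontinuation rule can leave primary-outcome data missing in one arm for a smoking-related reason, and the plan does not say how those participants are followed or analysed; direction unknown, size probably small

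*Combined protocol and SAP*

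**What the plan says.** The rule appears twice in the combined protocol and SAP. Protection Against Risk has "If participants in the VLNC condition are found to be smoking more than twice their usual cigarettes/day", adds a CO limit of 100 ppm, and says that those who meet either condition are "discontinued from the study protocol". The VLNC paragraph of Alternative Products and the Nicotine Patch has the same two triggers and the same consequence: "Participants found to be smoking more than twice their usual cigarettes/day or who demonstrate a CO" of 100 ppm or more.

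The VLNC paragraph gives the reason, which is possible compensatory smoking, and says "we will monitor compensatory smoking by examining both VLNCs smoked/day as well as carbon monoxide (CO) levels". VLNC participants "will be given enough VLNCs to completely substitute for their own cigarettes during the Switch Weeks" and can get more at later visits. The event is expected to be uncommon: "many studies have shown that smokers engage in minimal or no compensatory smoking".

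No matching rule is given for the other two arms, although Table 1 schedules smoking and CO assessments for all participants.

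Under Analytic Plan, "The primary outcome is the number of conventional cigarettes smoked during each Switch Week". The model is a mixed ANOVA with Product (three levels, between subjects) and Patch (two levels, within subjects). The only provision for missing data is under Visit assessments, where timeline follow-back fills gaps in the EMA record.

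**The concern.** The rule removes people from one randomised arm on the basis of behaviour seen after randomisation, and that behaviour is related to the primary outcome. A no-product participant with the same readings stays in.

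The wording points to leaving the study rather than only stopping a product. Elsewhere the plan separates the two. The Data and Safety and Monitoring Plan allows study products to be stopped after an adverse event, and Protection Against Risk lets participants with patch side effects reduce or drop the patch without saying that they leave.

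The rule could be met as early as Visit 2, after the practice week and before either Switch Week, so one or both primary-outcome weeks could be lost. A mixed ANOVA in its standard form uses only participants with both weeks. The plan names no as-randomised analysis set and no sensitivity analysis for these participants. At stake is whether the VLNC versus e-cigarette and VLNC versus no-product contrasts still compare the groups as randomised.

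**Working it through.** **Inputs from the plan** (Power for Primary Aim Hypotheses): 54 per group after attrition, SD 6, detectable between-arm difference 3.3 cigarettes. Alpha, sidedness, power and the unit (per day or per week) are not stated.

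**Reproducing the plan's figure.** Take two-sided alpha 0.05 (assumed). The standard error is 6 × √(2/54) = 1.155, and 3.3/1.155 = 2.858. The normal approximation gives 81.5% power and the noncentral t gives 80.8%. The difference detectable with 80% power is 3.26, which rounds to 3.3. The design figure is sound on these assumptions.

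**Size of a shift.** Let k of N = 54 VLNC participants be lost, and let D be the mean own-cigarette count of those lost minus that of those retained. Then observed mean − full mean = −(k/N) × D. The plan gives neither k nor D, so these values are assumed: k = 1, 2, 4, 8 and D = ±6 (1 SD) or ±12 (2 SD). For example, 2/54 × 6 = 0.22 and 4/54 × 12 = 0.89.

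Type I error is two-sided, from the noncentral t with SD 6 and 54 versus 54 − k participants. For k = 4 and a shift of 0.89, the standard error is 6 × √(1/54 + 1/50) = 1.178, so the noncentrality is 0.89/1.178 = 0.75.

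| k | Shift, size of D = 6 | Share of 3.3 | Type I error | Shift, size of D = 12 | Share of 3.3 | Type I error |
|---|---|---|---|---|---|---|
| 1 | 0.11 | 3% | 0.051 | 0.22 | 7% | 0.054 |
| 2 | 0.22 | 7% | 0.054 | 0.44 | 13% | 0.067 |
| 4 | 0.44 | 13% | 0.066 | 0.89 | 27% | 0.116 |
| 8 | 0.89 | 27% | 0.113 | 1.78 | 54% | 0.310 |

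A positive D lowers the observed VLNC mean, in favour of VLNCs. A negative D raises it by the same amount. A count cannot fall below zero, so a negative D cannot be larger in size than the retained mean, which the plan does not predict.

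**Sign of D.** Take a 20-per-day smoker, for whom the trigger is more than 40 per day.

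- If VLNCs count towards the trigger, 41 VLNCs and no own cigarettes meets it. This person has substituted completely, and the loss counts against VLNCs.
- If own and study cigarettes both count, and VLNC use stays within a supply matched to 20 per day, exceeding 40 needs more than 20 own cigarettes per day. This loss favours VLNCs.
- The CO trigger does not settle it. Visit assessments notes that VLNCs also produce CO.

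The VLNC paragraph monitors VLNCs per day and CO. Protection Against Risk refers to cigarettes per day without saying which. The two passages do not fix the sign.

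**The case against.** The asymmetry has a stated reason, since the rule addresses a risk specific to VLNCs. The event is expected to be rare, and one or two losses at 1 SD are negligible. Planned attrition is far larger: 1 − 54/75 = 28% per arm, assuming equal allocation of 225. The wording does not say that data already collected are discarded or that the 3-month call is cancelled. Nor does the Analytic Plan say that participants with one week are dropped. The reference list includes works on missing-data methods that the text never cites, so a method may have been intended.

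Much of this stands. It limits the size, and it means that loss from the analysis is inferred from the wording and the usual form of the model rather than stated. It does not supply a rule for these participants. General attrition may affect all arms, whereas this loss is confined to one by design.

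A reader might infer that the rule removes the heaviest smokers and so flatters VLNCs. The documents do not support that. Heavy total or VLNC smoking is not heavy own-cigarette smoking, and someone who meets the trigger may have an own-cigarette count of zero.

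**Conclusion.** The concern holds as a gap in follow-up and analysis: informative missingness can arise in the VLNC arm alone, with no as-randomised safeguard. The direction is unknown and the size is probably small, about 0.1 to 0.2 cigarettes for one or two losses at 1 SD. It becomes material only at around four losses of 54 at 2 SD (0.9 cigarettes, 27% of the design difference, type I error about 0.12). These sizes rest on assumed numbers lost and assumed differences, on SD 6, and on whichever unit the 3.3 is in. This is a cheap improvement rather than a flaw that undermines the trial, and it is no criticism of having a safety rule.

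**What to change.** Leave the safety trigger and the stopping of the product unchanged. Then:

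- State that participants who meet the rule are still asked for evening reports, timeline follow-back and the remaining contacts.
- Include them in their randomised arm in the primary analysis, using a mixed model that keeps participants with only one Switch Week. This compares the arms as assigned, whether or not the product was stopped.
- Report how many met the rule and at which visit.
- Add a sensitivity analysis in which the missing own-cigarette counts are set above and below those of retained participants, for example by 1 and 2 SD with a floor of zero. It is needed because a mixed model cannot recover someone with no Switch Week data.
- Reconcile the VLNC paragraph and Protection Against Risk on which cigarettes the trigger counts.

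If outcomes are obtained from everyone who meets the rule and analysed as randomised, the bias from removal is zero. The cost is a few sentences and a few extra contacts using the existing smartphone reports, visits and call. Some participants may decline, which is why the sensitivity analysis stays in.
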